### **Moments of electrical impedance tomography measurement**

Once the patient is connected to the tomograph, the quality of the signal must be checked. Once it is verified that it is being measured properly, that the patient is well positioned and that the signal is of high quality, the recording will begin. tomograph record; after the first

two minutes of calm breathing have elapsed, the first event will be marked, which will be recorded as "pre", and the use of the corresponding respiratory incentive will begin. The proper use of the device will be previously explained to you through a video that will illustrate the correct way to use it. The participant will receive visual feedback from the device when the condom is raised within the buretrol in the case of the IMP or when the spheres are raised in the branded incentive "Triflo II®"

Three series of ten breaths will be performed, with a 1-minute rest between series. In the last repetition of the third series, the second event will be marked, which will be recorded as "intra".

The maneuver will be finished once the series and repetitions are finished, removing the mouthpiece from the participant's mouth and they will be asked to continue breathing calmly for 2 minutes, after which the third event will be marked, which will be recorded as "post". And the recording of the record will be terminated.

At the beginning and at the end of the intervention, clinical data will be taken (heart rate, respiratory rate and oxygen saturation) and 15 minutes after finishing the test.

Taking into account that the subjects are using a device that is not used routinely in daily life, the perception of the subject in the use of each of the devices will be evaluated to know the degree of comfort of these by means of the scale of Likert and in the same way it will be valued if I generate perception of dyspnea by means of the Borg scale

The session may be interrupted if the participant does not wish to continue with the intervention, if the participant shows intolerance to the maneuver, if the respiratory rate is greater than 25 breaths per minute and if there is use of accessory muscles.

After each measurement is finished with each participant, the equipment will be disinfected

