## Methods

### Study Design

Crossover clinical trial, in which the measurement of the distribution of pulmonary ventilation by means of EIT will be evaluated, during the use of a Branded flow respiratory incentive “Triflo II®” and the IMP, in a sample of healthy volunteers from the city of Santiago de Cali. Both incentives will be used on all participants, and the order of assignment will be randomized.

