### Population Sample

Sample size of 18 subjects (9 men, 9 women) healthy volunteers from the Municipality of Santiago de Cali. The type of sampling will be non-probabilistic for convenience.

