### Main variables:

- EELI Delta ( $\Delta$ EELI): Measures the change in the average end-expiratory pulmonary impedance before and after an intervention.
- MTV ROI: Minute regional tidal variation

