### **Randomization**

The randomization to choose which will be the first incentive that each participant will use and to which the first ventilation measurement will be carried out by means of EIT, will be carried out by simple randomization, through the "RANDOM.ORG" program (<https://www.random.org/lists/>) and <http://www.jerrydallal.com/random/permute.htm>

These measurements will be made at the facilities of the Universidad del Valle, according to availability. The first measurement will be carried out with the incentive that has been randomly assigned to the participant, the second measurement will be carried out one week after the first measurement was made with the other incentive, with the objective that the washing period is fulfilled, both measurements will be performed by the principal investigator. For the measurement of the EIT, the instructions defined in standard operating procedure 3 will be followed and for the application of the protocol for the use of incentives, the instructions defined in standard operating procedure 6 and 7 will be followed according to the corresponding incentive. The duration of this procedure will be approximately 30 minutes for each measurement.

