## **Phase 4: Statistical analysis**

### Descriptive Analysis

The registration of the information will be carried out in the data collection formats designed for this purpose. To then be organized in the Microsoft Excel program. In order to have an initial knowledge of the behavior of each of the variables.

Quantitative variables will be presented as mean and standard error, and qualitative variables as frequencies and percentages. Normality tests (D'Agostino Pearson) will be applied to identify data distribution; subsequently, a paired T test will be performed to identify if the changes obtained after the interventions are statistically significant ( $p$  less than 0.05). For the statistical procedure, GraphPad Prism version 7.0 will be used.

For the EIT data, the monitoring sessions will be recorded with the participant's code, each recording will be transferred to a USB to be downloaded to the equipment where the information collected is stored for the reconstruction of the impedance measurement through the tool (Electrical Impedance Tomography Data Analysis Tool v6.3, Dräger Medical). This Reconstruction will allow us to isolate the main areas of interest (EIT measurement times) and quantify the percentage changes in EELI in response to lung expansion with respiratory incentive.

Anexo 1. Approval by a human subjects protection review board

Proyecto: **“DISTRIBUCIÓN DE LA VENTILACIÓN PULMONAR CON EL INCENTIVO MODIFICADO DE PACHÓN VS OTRO INCENTIVO RESPIRATORIO COMERCIAL, A TRAVÉS DE TOMOGRAFÍA DE IMPEDANCIA ELÉCTRICA, EN POBLACIÓN SANA DE LA CIUDAD DE CALI”**

Investigador Principal: **“[name]/ [name]/ [name]”**

Código Interno: (031-022)

Fecha en que fue sometido:

DIA	MES	AÑO
16	05	2022

El Consejo de la Facultad de Salud de la Universidad del Valle, ha establecido el Comité de Ética en Investigación en Salud (CEIS), el cual está regido por la Resolución 008430 del 4 de octubre de 1993 del Ministerio de Salud de Colombia por la cual se establecen las normas científicas, técnicas y administrativas para la investigación en salud; los principios de la Asamblea Médica Mundial expuestos en su Declaración de Helsinki de 1964, última revisión en 2013; y el Código de Regulaciones Federales, título 45, parte 46, para la protección de sujetos humanos, del Departamento de Salud y Servicios Humanos de los Institutos Nacionales de Salud de los Estados Unidos 2000. Este Comité certifica que:

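### The session *pre* value enters ΔEELI only by subtraction or percentage change, MTV ROI has no stated baseline handling, and no baseline-adjusted between-device comparison is specified

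*Combined protocol and SAP*

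**What the plan says.** The trial is a two-period crossover: "Both incentives will be used on all participants, and the order of assignment will be randomized" (Study Design). The sample is given as "Sample size of 18 subjects (9 men, 9 women) healthy volunteers" (Population Sample). The sessions are separated in time: "the second measurement will be carried out one week after the first measurement was made with the other incentive" (Randomization).

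Each session is one continuous EIT recording with three marked events, *pre*, *intra* and *post*. For the first, "the first event will be marked, which will be recorded as 'pre" (Moments of electrical impedance tomography measurement). *Intra* is marked at the last repetition of the third series, and *post* after two further minutes of calm breathing.

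There are two main variables. The first, ΔEELI, is defined thus: "Measures the change in the average end-expiratory pulmonary impedance before and after an intervention". The second is listed only as "MTV ROI: Minute regional tidal variation" (Main variables), with no reference to a baseline.

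Under Descriptive Analysis, "a paired T test will be performed to identify if the changes obtained after the interventions are statistically significant", with p "less than 0.05". The same section says that the reconstruction will quantify percentage changes in EELI. The plan names no covariate, model, order term or confidence interval.

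**The concern.** The trial asks how the two devices compare, in 18 people. Pairing removes stable differences between people. It does not remove differences between one person's two sessions, held a week apart. The electrode belt is presumably refitted for the second session; that is an inference, as the protocol does not say so. The *pre* value carries information about those session differences and is already recorded.

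The plan uses that information in a fixed way or leaves its use open. An absolute change score forces a slope of 1 on *pre*; an analysis that ignores *pre* forces a slope of 0. For MTV ROI the plan does not say which applies. For EELI it leaves absolute and percentage change both possible. It also does not say whether the paired t test compares *pre* with *post* within a device or compares changes between devices.

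Two things are at stake: the precision of the device contrast, and whether an explicit device contrast is prespecified at all. The hypotheses are about similarity, so an estimate with an interval is needed.

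**Working it through.** The plan gives no power, SD, effect size or margin, so there is no stated figure to reproduce. The check compares the variance of three estimates of the IMP minus Triflo II difference.

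**Inputs**
- n = 18, each using both devices (Population Sample, Study Design).
- r: correlation, across people, between the device difference in *pre* and the device difference at the later time point. Not in the documents; assumed range 0.3 to 0.9.
- k: SD of the *pre* difference divided by SD of the later difference. Not in the documents; k = 1 first, then k = 0.5 as an illustration.

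**Formulas**, in units of the variance of the later difference, absolute scale:
- ignoring *pre*: 1
- change score: 1 + k² − 2rk, which is 2(1 − r) when k = 1
- adjusted for the *pre* difference, with an order term: (1 − r²)(1 + 1/(n − 4)) = (1 − r²)(15/14)

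The factor 15/14 = 1.071 is the price of estimating the slope.

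**Equal variances (k = 1)**

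| r | Change score | Adjusted | Adjusted / change | Adjusted / ignoring *pre* |
|---|---|---|---|---|
| 0.3 | 1.40 | 0.91 × 1.071 = 0.975 | 0.70 | 0.98 |
| 0.5 | 1.00 | 0.75 × 1.071 = 0.804 | 0.80 | 0.80 |
| 0.7 | 0.60 | 0.51 × 1.071 = 0.546 | 0.91 | 0.55 |
| 0.9 | 0.20 | 0.19 × 1.071 = 0.204 | 1.02 | 0.20 |

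A simulation of 40,000 trials per row, with 9 people in each order, agrees with these ratios to within 0.01. With the lost degrees of freedom charged, the mean 95% interval width relative to a paired t test on changes is 0.84, 0.90 and 0.96 at r = 0.3, 0.5 and 0.7.

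**Break-even points**
- Against the change score with k = 1: (1 + r)/2 × 15/14 = 1, so r = 28/15 − 1 = 0.87. Above that the change score is slightly better.
- Against ignoring *pre*: 1 − r² = 14/15, so |r| = √(1/15) = 0.26. Below that adjustment loses slightly, by at most 7% at r = 0.

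**Unequal variances (k = 0.5)**

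The change-score variance becomes 1.25 − r. Adjusted relative to change:
- r = 0.3: 0.975/0.95 = 1.03
- r = 0.5: 0.804/0.75 = 1.07
- r = 0.7: 0.546/0.55 = 0.99

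The best slope is r/k = 2r, which is exactly 1 at r = 0.5, so there the change score is already optimal and adjustment pays its full 7%. The comparison with ignoring *pre* does not depend on k.

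**Other costs**
- Residual degrees of freedom fall from 17 to 15: one for *pre*, one for order.
- Randomization is simple, so the order groups may be unequal. Averaging the two order groups equally multiplies the variance by (18/4)(1/n₁ + 1/n₂). A 9:9 split gives 1; a 12:6 split gives 4.5 × (1/12 + 1/6) = 1.125, a further 12.5%.

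**The case against.** A reader might infer that *pre* goes unused. The documents do not support that for the first main variable: ΔEELI is itself a change from *pre*, the test is on changes, and percentage changes in EELI are planned. For EELI the issue is how *pre* is used; only for MTV ROI is its use unstated.

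A reader might also infer that session differences in starting level pass straight into the SD of the paired difference. An offset shared by *pre* and *post* cancels in an absolute change score. Because both values come from one recording, a belt shift would tend to move them together, pointing to a high r, where the change score does well: with equal variances the ratio is 0.36 × 1.071/0.40 = 0.96 at r = 0.8, and 1.02 at r = 0.9.

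Equal variances are doubtful at *intra*, which is marked during incentive breathing while *pre* is calm breathing. The k = 0.5 example removes the gain over the change score almost entirely for r from 0.3 to 0.7; other SD ratios could favour adjustment. The algebra is for absolute differences and does not carry over to percentage change.

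Finally, the missing similarity margin and the unclear between-device test are larger gaps than the choice of covariate.

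All of this stands and limits the size of the gain. It does not remove the case for the change. A slope fixed at 1 or 0 can lose much more than the 7% that estimating it costs, r and k are unknown, and the proposed model supplies the between-device estimate that the plan lacks.

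**Conclusion.** The point holds in a limited form. ΔEELI uses *pre* only by subtraction or percentage change, MTV ROI has no stated baseline handling, and the single planned test is not clearly a device comparison.

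If variances are equal and the outcome is an absolute change, adjustment reduces variance by about 30%, 20% and 9% at r = 0.3, 0.5 and 0.7, and increases it by about 2% at r = 0.9. Against an analysis that ignores *pre*, the reductions are about 2%, 20% and 45% at r = 0.3, 0.5 and 0.7. If variances are unequal, the gain over a change score may disappear. These figures rest on assumed values of r and k.

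It is tempting to express the result as a firm number of participants lost from 18, or to call the gain free. The documents give neither the correlation nor the SDs, and the adjustment has real if small costs, so neither statement is supported. This is a cheap improvement that also makes the device comparison explicit.

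**What to change.** In Phase 4, Descriptive Analysis, for each main variable:
- Name one time point for the device comparison, *intra* or *post*, and one scale for EELI.
- Regress the within-person IMP minus Triflo II difference at that time point on the within-person IMP minus Triflo II difference in *pre*, with a centred term for order (coded −½ and +½).
- Report the adjusted mean difference at zero *pre* difference, with its 95% confidence interval, as the device comparison in place of the paired t test.

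The cost is analysis wording only; the plan already collects the data. Statistically it uses two residual degrees of freedom (17 to 15), at most about 7% extra variance for the slope, and some further loss if the order groups are unequal (12.5% for a 12:6 split). The model does not supply a similarity margin, which must be stated separately.

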#### **Quality control:**

1. To guarantee the quality of the registered information, the main investigator will carry out random reviews in which he will corroborate the coherence between the original information of the tomographer, that of the registration in the formats and that of the database. The detected errors will be corrected.
2. An external person to the study, who will not participate in the measurements, will randomly review the forms once every 15 days to verify the information before entering it into the database. Additionally, once a month a meeting will be held with the research group in order to socialize project progress

## **Phase 4: Statistical analysis**

### Descriptive Analysis

The registration of the information will be carried out in the data collection formats designed for this purpose. To then be organized in the Microsoft Excel program. In order to have an initial knowledge of the behavior of each of the variables.

Quantitative variables will be presented as mean and standard error, and qualitative variables as frequencies and percentages. Normality tests (D'Agostino Pearson) will be applied to identify data distribution; subsequently, a paired T test will be performed to identify if the changes obtained after the interventions are statistically significant ( $p$  less than 0.05). For the statistical procedure, GraphPad Prism version 7.0 will be used.

For the EIT data, the monitoring sessions will be recorded with the participant's code, each recording will be transferred to a USB to be downloaded to the equipment where the information collected is stored for the reconstruction of the impedance measurement through the tool (Electrical Impedance Tomography Data Analysis Tool v6.3, Dräger Medical). This Reconstruction will allow us to isolate the main areas of interest (EIT measurement times) and quantify the percentage changes in EELI in response to lung expansion with respiratory incentive.

Anexo 1. Approval by a human subjects protection review board

Proyecto: **“DISTRIBUCIÓN DE LA VENTILACIÓN PULMONAR CON EL INCENTIVO MODIFICADO DE PACHÓN VS OTRO INCENTIVO RESPIRATORIO COMERCIAL, A TRAVÉS DE TOMOGRAFÍA DE IMPEDANCIA ELÉCTRICA, EN POBLACIÓN SANA DE LA CIUDAD DE CALI”**

Investigador Principal: **“[name]/ [name]/ [name]”**

Código Interno: (031-022)

Fecha en que fue sometido:

DIA	MES	AÑO
16	05	2022

El Consejo de la Facultad de Salud de la Universidad del Valle, ha establecido el Comité de Ética en Investigación en Salud (CEIS), el cual está regido por la Resolución 008430 del 4 de octubre de 1993 del Ministerio de Salud de Colombia por la cual se establecen las normas científicas, técnicas y administrativas para la investigación en salud; los principios de la Asamblea Médica Mundial expuestos en su Declaración de Helsinki de 1964, última revisión en 2013; y el Código de Regulaciones Federales, título 45, parte 46, para la protección de sujetos humanos, del Departamento de Salud y Servicios Humanos de los Institutos Nacionales de Salud de los Estados Unidos 2000. Este Comité certifica que:

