### Specific Objectives:

- Describe the sociodemographic, anthropometric, clinical and spirometric characteristics of the study participants.
- Determine the global and regional pulmonary impedance through the EIT during the use of the IMP.
- Determine the global and regional pulmonary impedance through the EIT during the use of the Triflo II®.

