#### Alternate Hypothesis

YES, the distribution of pulmonary ventilation, measured by EIT, between the IMP and the branded flow incentive “Triflo II®” in healthy volunteers of the City of Cali, is similar.

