### Distribution Age Ranges

Age Range	Men	Wome
18 – 34	3	3
35 – 50	3	3
51 – 65	3	3

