### Selection criteria

#### Inclusion criteria:

- People aged between 18-65 years

- People with clinical stability, defined as the absence of any acute illness during the previous 6 weeks and a Charlson index score of 0-1 (12% mortality/year- no comorbidity)
- People with a body mass index (BMI) of 18.5 – 35 Kg/m^2(52,53)
- People without mental or cognitive alterations
- People who accept informed consent

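### The plan aims to support similarity of the IMP and Triflo II but commits to no estimate or interval for the paired device difference; standard errors also do not describe the participants

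*Combined protocol and SAP*

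**What the plan says.** All references are to the combined protocol and SAP.

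- Phase 4, Descriptive Analysis: "Quantitative variables will be presented as mean and standard error". No exception is made for participant characteristics or for the EIT outcomes.
- The same section, after normality testing: "a paired T test will be performed to identify if the changes obtained after the interventions are statistically significant", with p less than 0.05 as the criterion. The sentence does not say whether the pairs are before and after one device, or IMP against Triflo II.
- The General Objective is to compare the two devices. The Alternate Hypothesis is that the distribution of ventilation with the two devices, "in healthy volunteers of the City of Cali, is similar".
- The first specific objective is purely descriptive: "Describe the sociodemographic, anthropometric, clinical and spirometric characteristics of the study participants". The others are set per device, for example "Determine the global and regional pulmonary impedance through the EIT during the use of the IMP".
- Population Sample: "Sample size of 18 subjects (9 men, 9 women) healthy volunteers". Under Study Design, every participant uses both devices, so complete data give 18 pairs.

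The public text plans no standard deviation, interquartile range, range or confidence interval, either for single variables or for the device difference.

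**The concern.** There are two consequences of unequal weight.

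**Device comparison (main point).** A claim of similarity rests on the size of the difference that remains compatible with the data. The planned outputs are a mean and SE for each device, plus a test result. In a crossover, the two per-device SEs do not determine the SE of the within-participant difference. A result described as not significant can come from a tight interval around zero or from a wide one. Followed as written, the plan could leave a non-significant p as the main support for calling the devices similar, with no statement of how different they might still be. It is also unclear whether the planned test compares devices at all.

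**Participant description (secondary).** The SE measures how precisely a mean is estimated, not how much people differ. A reader who takes it for spread will think the sample more homogeneous than it is.

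**Working it through.** **Inputs.** n = 18 (Population Sample); both devices used by all (Study Design); age quotas of 3 men and 3 women in each of 18–34, 35–50 and 51–65, so 6 per band ("Distribution Age Ranges"); BMI limits 18.5 to 35 (Inclusion criteria); threshold 0.05, taken as two-sided because the plan does not say. The documents give no SD, correlation or margin. The only internal check on the sample size is the quota table: 6 cells × 3 = 18, which agrees.

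**1. Interval for the device difference.** The 95% half-width is t(0.975, 17) × SD_diff / √18 = 2.110 × SD_diff / 4.243 = 0.497 × SD_diff.

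**2. Why per-device SEs are not enough.** If both devices have the same SD and the within-person correlation is ρ, then SD_diff = SD × √(2(1 − ρ)). The documents do not give ρ, so I assume a range:

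| Assumed ρ | SD_diff / SD | 95% half-width, in SDs of a single measurement |
|---|---|---|
| 0 | 1.414 | 0.70 |
| 0.5 | 1.000 | 0.50 |
| 0.9 | 0.447 | 0.22 |

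The same pair of per-device SEs is therefore compatible with intervals that differ about threefold in width (0.70 / 0.22 = 3.2).

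**3. What a non-significant p leaves open.** The half-width divided by the absolute mean difference is 2.110 / t, where t is the paired t statistic on 17 degrees of freedom:

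| Two-sided p | t | Half-width ÷ observed difference |
|---|---|---|
| 0.05 | 2.110 | 1.00 |
| 0.06 | 2.015 | 1.05 |
| 0.20 | 1.333 | 1.58 |
| 0.50 | 0.689 | 3.06 |

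If only p above 0.05 is shown, the reader knows that the half-width exceeds the observed difference, but not by how much. Given the observed mean difference, an exact between-device p or the SE of the difference supplies the missing quantity.

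**4. SE against SD for description.** SE = SD / √n, so SD = √18 × SE = 4.24 × SE. The factor is 4.12 at n = 17 and 4.00 at n = 16.

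- *Age, smallest SD, in completed years:* 6 at 34, 6 at 42, 6 at 51. Mean 42.33; sum of squares 868; SD = √(868/17) = 7.15; SE = 1.68. With exact ages (just under 35, 43, 51) the minimum falls to about 6.7.
- *Age, largest SD, in completed years:* 6 at 18, 2 at 35, 4 at 50, 6 at 65. Mean 42.67; sum of squares 6976; SD = √(6976/17) = 20.26; SE = 4.77. Putting the whole middle band at 35 gives 19.99, and at 50 gives 20.17.
- *BMI, largest SD:* 9 at 18.5 and 9 at 35. Sum of squares 18 × 8.25² = 1225.1; SD = √(1225.1/17) = 8.49; SE = 2.00.

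The age quotas thus imply an SD of about 7.1 to 20.3 years, which the table would show as 1.7 to 4.8.

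**The case against.** **The SD can be recovered.** A labelled mean and SE with n is a complete summary, and SD = SE × √n. This stands. The description half is a reporting matter: it changes neither the t test nor any conclusion, and would not justify a comment on its own. A reader might infer that the spread is lost or the analysis invalidated, but the documents do not support that. Recovery does not help the device comparison, however, because per-device SEs do not yield the SE of the paired difference.

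**The 0.05 criterion is a decision threshold, not a reporting rule.** This also stands. The plan nowhere says that p values will be shown only as above or below 0.05, so it would be wrong to infer that the interval will certainly be unobtainable. If exact between-device p values appear beside the mean differences, the interval can be worked out. The point is that the plan commits to neither an exact p nor the SE of the difference, and does not clearly commit to a between-device test.

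**An interval does not settle similarity.** Correct. The plan states no margin, so a confidence interval shows what difference remains possible but cannot by itself declare the devices similar. The missing margin is a separate question that this change does not resolve.

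**Conclusion.** The point holds as a modest, nearly free improvement. The plan seeks to support similarity, yet commits to no estimate or interval for the IMP minus Triflo II difference. With 18 complete pairs the 95% half-width would be 0.497 × SD of the paired differences. For non-significant results it can range from just over the observed difference to several times it (3.06 times at p = 0.50). These figures assume a two-sided paired t analysis with all 18 participants complete; the correlation range of 0 to 0.9 is an assumption.

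The use of SE for description is secondary and affects presentation only. It understates spread by a factor of 4.24 for a reader who mistakes it for SD. The age bounds rest on filled quotas and ages in completed years.

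The documents do not support a reading in which the comparison cannot be interpreted whatever is reported, or in which adding an interval would by itself establish similarity.

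**What to change.** In Phase 4, Descriptive Analysis:

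1. Add: *For delta EELI, and for MTV ROI in each region of interest at each analysed time point, the IMP minus Triflo II comparison will be a paired analysis of the within-participant difference, reported as the mean difference with its 95% confidence interval and exact p value. A non-significant p value alone will not be taken as evidence of similarity.*
2. Reword the paired t test sentence so that it names this same between-device contrast. Otherwise the interval could sit beside a p value for a different question.
3. Replace the summary sentence with: *Quantitative variables will be presented as mean and standard deviation, or median and interquartile range if skewed; qualitative variables as frequencies and percentages.*

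The regions and time points for MTV ROI need to be listed, because the section on EIT measurement moments marks three events (pre, intra, post) and the plan does not say which are analysed.

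The cost is a few sentences and slightly longer tables. No new data or participants are needed, since every quantity comes from measurements already planned.

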### Hypothesis

#### Null Hypothesis:

The distribution of pulmonary ventilation, measured by EIT, between the IMP and the Triflo II® in the healthy volunteers of the City of Cali, is NOT similar.

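### The hypotheses ask the trial to demonstrate similarity, but the only comparative test is a paired t-test of zero difference or zero change with no margin, so it cannot support that conclusion

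*Combined protocol and SAP*

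**What the plan says.** - **Hypothesis section.** Under the null, ventilation distribution measured by EIT, compared "between the IMP and the Triflo II® in the healthy volunteers of the City of Cali, is NOT similar". Under the alternative, the distribution "in healthy volunteers of the City of Cali, is similar". Similarity is therefore the claim to be established.
- **General Objective.** To compare the distribution of ventilation during use of the two devices. The Specific Objectives on EIT then list each device separately.
- **Study Design.** A crossover: "Both incentives will be used on all participants, and the order of assignment will be randomized". Population Sample gives 18 participants, so there are 18 pairs.
- **Main variables.** Delta EELI, described as "Measures the change in the average end-expiratory pulmonary impedance before and after an intervention", and a second variable given as "MTV ROI: Minute regional tidal variation".
- **Descriptive Analysis (Phase 4).** After a normality check, "a paired T test will be performed to identify if the changes obtained after the interventions are statistically significant", with significance set at p below 0.05. This is the only comparative test named. The section does not say which two quantities are paired, and it ties the p-value to neither hypothesis.
- **Not found in the text supplied.** A margin for similarity, two one-sided tests, a confidence-interval rule, or any other criterion for concluding that the devices are similar.

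**The concern.** A test can support an alternative only by rejecting the matching null. The Hypothesis section has an equivalence structure: dissimilarity must be rejected before similarity is claimed. A paired t-test has the opposite null, zero difference or zero change, so rejecting it can never yield the stated alternative.

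As planned, a statement that the low-cost device ventilates the lung similarly to the branded one would have to rest either on a non-significant p-value or on two separate pre/post results set side by side. Neither controls the probability of declaring similarity falsely. With a small sample the first is also easy to obtain, because imprecision alone produces non-significance. And since the pairing is undefined, the reading could be chosen after the data are seen.

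**Working it through.** **1. What each reading can conclude.** Let D be the within-person difference, IMP minus Triflo II, in a main variable.

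| Reading of the t-test | Null tested | If p < 0.05 | If p ≥ 0.05 |
|---|---|---|---|
| Between devices | mean D = 0 | devices differ (contradicts the alternative) | no difference detected; similarity not shown |
| Pre/post within each device | mean change = 0, per device | that device changes the variable | no change detected for that device |

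No cell supports the stated alternative. This step is logical and needs no assumed number.

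**2. Inputs for the size of the problem.** From the documents: 18 pairs and a 0.05 level. Assumed, because the documents give none of them: a two-sided test, the true effects, the margins and the correlations. Effects and margins are in units of SDd, the SD of D. The plan gives no power, effect size or SD for its 18 participants, so there is no planned figure to reproduce.

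**3. Between-device reading.** P(p ≥ 0.05) is the probability that a noncentral t variable with 17 degrees of freedom and noncentrality δ√18 lies within ±2.110, where δ is the true difference divided by SDd.

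| True difference (SDd) | 0.3 | 0.4 | 0.5 | 0.75 | 0.9 | 1.0 |
|---|---|---|---|---|---|---|
| Non-significant | 78% | 64% | 48% | 15% | 5% | 2% |

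These are false claims of similarity only if non-significance is read that way and the difference in question matters. The missing margin is what would settle the second point.

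**4. Pre/post reading.** Simulated trials of 18, equal SD of change for both devices, correlation 0.3 to 0.7 between devices:

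- Both devices truly change by 0.5 SD, so they are identical: exactly one is significant in about 26% (correlation 0.7) to 41% (correlation 0.3) of trials.
- One device changes by 1.0 SD and the other by 2.0 SD: both are significant in about 98% of trials.

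This reading can suggest a difference where there is none, and sameness where there is a large difference.

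**5. What a valid similarity test would deliver with 18 pairs.** Similarity is concluded if mean D ± 1.740 × s/√18 (the 90% CI, s being the sample SD of D) lies wholly inside ±M. The expected half-width is about 1.740/√18 = 0.41 SDd. Power at a true difference of zero, by integration over the sampling distribution of s:

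| Margin M (SDd) | 0.5 | 0.6 | 0.7 | 0.75 | 1.0 |
|---|---|---|---|---|---|
| Power | 31% | 58% | 77% | 84% | 98% |

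Power reaches 80% at M = 0.72 SDd. For 80% power at narrower margins, 36 pairs are needed at 0.5 SDd and 55 at 0.4 SDd.

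If both main variables must pass, power lies between the independent and the fully correlated case: 0.315² = 10% to 31% at 0.5 SDd, and 0.8405² = 71% to 84% at 0.75 SDd.

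Adding a period term costs almost nothing if nine participants start on each device (31% and 84% at those two margins). At a 12:6 split, power falls to about 24% and 78%.

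**The case against.** The strongest reply is that the general objective is only to compare, that similarity is used loosely, and that the natural reading of the test is between devices: the design is a crossover and Delta EELI is already a before/after change, so the paired changes would be the IMP change and the Triflo II change. On that view the pre/post reading carries little weight. Nor does any passage say that a non-significant result will be read as similarity.

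Part of this stands. The between-device reading is plausible and may be intended. The pre/post reading is an ambiguity rather than an established plan, though the device-by-device specific objectives and the pre, intra and post marks in the EIT procedure mean it cannot be excluded. Misuse of a non-significant result is a risk, not a written rule. A device difference with its CI would meet the general objective.

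None of this rescues the mismatch, because the between-device reading cannot support the alternative either, and these are the trial's only stated hypotheses.

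Two cautions on the power figures also stand. The Randomization section specifies simple randomization (while also citing a permutation web page), and true simple randomization of 18 gives a split other than 9:9 in about 81% of trials and 12:6 or worse in about 24%. And the regional variable may mean several regions, in which case requiring all to pass could have less power than the two-variable range shown.

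**Conclusion.** The concern holds and must be fixed before analysis. The plan's only comparative test cannot establish its stated alternative on either reading; this is a contradiction between the Hypothesis and Descriptive Analysis sections, not a missing detail. That conclusion rests on no assumed number, and a one-sided test of zero difference would not change it.

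The percentages are illustrations, not measurements of error in this trial. They rest on assumed effects, margins and correlations, normal differences and 18 complete pairs. Within those limits, a between-device difference of half an SDd would go undetected in about half of such trials. A proper similarity test with 18 pairs is adequately powered only for wide margins.

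**What to change.** In Descriptive Analysis:

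1. Define the analysed quantity as the within-person IMP minus Triflo II difference in Delta EELI and in MTV ROI, or in one of them named as primary. State the scale (the section also mentions percentage changes in EELI) and which regions are analysed.
2. Report the difference with its 95% CI, preferably from a crossover model with a period term, since order is randomized.
3. Conclude similarity only if the 90% CI lies wholly inside ±M for that variable. Fix each M before the data are analysed and justify it on substantive grounds. The five-person pilot is planned for instrument handling and timing, and its SD would not be a basis for M. If both variables are kept, require both to pass.
4. If no M can be justified, report the difference with its 95% CI, reword the hypotheses to match, and drop the similarity claim.

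**Cost.** Option 4 costs only rewording and changes no data collection. The margin route makes similarity harder to claim: unless a margin of about 0.72 SDd or wider can be defended, it means a larger trial or a probable failure to show similarity.
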